ESG is a commonly performed procedure that has been shown to demonstrate significant weight loss. However, combining it with HAPC technique to enable approximation of submucosal surfaces for enhanced gastroplasty healing, durability of this procedure could be enhanced. This could help maximize the metabolic benefits of gastric mucosal revitalization in conjunction with the restrictive effects of ESG for enhanced weight loss, durability, and metabolic benefits of the combined procedure while minimizing the risk of weight recurrence previously reported with the traditional ESG.

STUDY OBJECTIVES

Assess the safety and durability of combined HAPC and ESG compared to traditional ESG

Assess weight loss and improvement in obesity related co-morbidities in combined HAPC and ESG compared to ESG alone.

STUDY DESIGN

General Description

This is a single-center, randomized, single-blinded clinical trial evaluating the efficacy and safety of combined HAPC and ESG for weight loss and improvement in obesity-related co-morbidities compared to ESG alone in participants with a BMI ≥ 30 and ≤ 40 kg/m² who have failed to achieve and maintain weight loss with a non-surgical management.

Participants will be recruited from outpatient clinical weight loss clinics and from study-related institutional review board (IRB) approved advertisements.

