Twenty-four eligible participants will be block-randomized 1 to 1 treatment (12 participants) and control (12 participants) groups. All participants will undergo endoscopy and those without endoscopic contraindications will be eligible. All treatment group subjects will undergo combined HAPC and ESG where APC is applied according to on-label use prior to the standard ESG technique for enhanced fibrosis along the site of the plications potentially providing an avenue for longer and more durable ESG while minimizing the associated complications. Control subjects will undergo traditional ESG alone. All participants will undergo a repeat upper endoscopy at 26 weeks (6 months) +/- 2 weeks to evaluate the durability of the endoscopic sutures. All subjects will undergo research MRI at baseline and 26 weeks +/- 2 weeks to evaluate and grade the durability of the created gastroplasty, gastric motility, and gastric accommodation. This specially developed MRI protocol at Mayo offers a gold standard in evaluating gastroplasty durability. Additionally, at both baseline and 26 weeks +/- 2 weeks, all patients will undergo gastric scintigraphy to evaluate and measure gastric emptying.

Endpoints Effectiveness

Primary:

- Assess durability of endoscopic plications and sutures 26 weeks (6 months) +/- 2 weeks post procedure between patients receiving HAPC/ ESG vs traditional ESG alone.

Secondary:

- %TBWL in the combined HAPC and ESG group compared to traditional ESG at 6 and 12 months.
- Assess the procedure safety.
- % Excess weight loss (EWL) at 6 and 12 months between both groups.
- Proportion with $\geq 25\%$ EWL at 6 and 12 months by randomized arm.
- % of patients in the combined HAPC and ESG group achieving $\geq 5\%$ TBWL at 6 and 12 months compared to ESG alone.
- % of patients in the combined HAPC and ESG group achieving $\geq 10\%$ TBWL at 6 and 12 months compared to ESG alone.
- Changes in quality of life assessed using standard validated questionnaires (IWQOL-lite and SF-36) at 6 and 12 months compared to baseline.
- Changes in depression assessed using PHQ-9 questionnaire at 6 and 12 months compared to baseline.

- Improvement/reduction of hunger and desire to eat evaluated using validated self-reported ratings of appetite based on a 100-mm visual-analogue scale at 6 and 12 months compared to baseline.
- Improvement in eating behaviors evaluated using the Three Factor Eating Questionnaire (TFEQ) at 6 and 12 months compared to baseline.

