^a Childbearing potential to be defined as women who are not yet post-menopausal who are not consistently utilizing an acceptable form of contraception. Acceptable forms of contraception to include hormonal methods such as oral contraceptives, patches, injections, vaginal ring, or implants, hormonal or copper intrauterine device, or history of surgical sterilization including tubal ligation or hysterectomy.

screening assessments will have the chance to review any questions with the study staff, as well as a recap of the follow-up schedule, and they will then receive their randomization assignment.

Recruitment efforts will be made by working with Mayo Clinic's Research Recruitment Services to develop marketing materials including a recruitment flyer in both print and digital formats, a social media recruitment plan leveraging Mayo Clinic's enterprise social media accounts for recruitment and other potential tactics to be determined after recruitment begins, directed towards the goal of boosting minority inclusion to be at least representative of the local population. Data will be pulled during the time of IRB submission and included to establish general targets justifying Exclusion #35 to help reserve spots for enrollment that are in-line with a representative population if they are not met by a certain threshold. At the time of this writing, Rochester, MN has demonstrated approximately 10% minority population.

Randomization

Participants will be randomly assigned to treatment or control group with a 1:1 allocation per a computer-generated randomization using variable block randomization.

Participants will be blinded to the results of randomization. They will remain blinded until the end of the study, or if there is medical or surgical safety concern. If any SAEs occur, subjects may be unblinded as defined by the Clavien-Dindo Grade III or above. Unblinding of subjects will be reported to IRB per local site IRB guidelines, if not meeting the criteria above. Measures will be taken to minimize or avoid bias in the study using "masking/blinding procedures." Randomization assignment will be recorded in the EDC and subject tracking, but will not be recorded within the EMR to reduce clinical team exposure to their randomized status for follow-up care. Research teams will not be blinded to the randomization results. Subjects will be asked to confirm with their study team if they have become aware of the procedure.

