All patients will undergo a standard moderate intensity life-style intervention administered over 12 visits in the first year after procedure. Participants will be required to follow up with their prescribing physician to make any necessary changes to their hypertension and/or type II diabetes medications at 3, 6, 9 and 12 months. Completion of patient follow-up with providers for medication adjustment will be captured with completion of the appropriate CRF at the corresponding visits. In the event that participants are unable to contact their physician or participants are experiencing symptoms related to the medication dosing requiring urgent action, the study team will make any necessary changes in their medication dosing and document these changes appropriately in the relevant CRFs. Any medication changes will be monitored and recorded by the study team. Laboratory testing will be obtained as detailed in the study schedule of events

Participants will return for follow-up visits per the schedule of events below. For all visits with the exception of weeks 1 and 4, an in-window visit will be considered as reporting for follow-up visits within a two-week window of the visit date.

At the time of the 6-month visit, each subject's 6-month de-identified EGD video will be shared with an external center for an additional blinded assessment of the primary endpoint (suture durability) by a qualified endoscopist. Each video will be classified objectively according to the aspect of the gastric tissue and the sutures (intact, partially intact, or open). This sharing will take place through Mayo SimpleShare system.

Schedule of Events (SOE)

Study Activity	Screening & Enroll.	Rand.	Procedure	Post-Op Call	Week 1	Week 4	Week 8	Week 12	Weeks 16, 20	Week 26 (Month 6)	Weeks 30, 36, 42, 48	Week 52 (Year 1)	Unscheduled Visit
Visit Number	-2	-1	0	1	2	3	4	5	6,7	8	9,10,11,12	13	
In-Window Day Range	45 to Rand.	60 to Proc.	00		+/- 2	+/- 3				+/- 14			
Informed Consent Form (ICF)	X												
Complete Physical Exam (CPE)*	X											X	X
Focused Physical Exam *					X								
EKG	X												
Formal nutritional assessment	X												
Formal psychology evaluation	X												
Pregnancy test **	X												
Laboratory tests ⁺	X										X		X
H-Pylori breath test (baseline only)													
Questionnaires ++	X							X		X		X	
Inclusion/Exclusion	X												
Procedure Assessment Form			X										
GERD Questionnaire & Activity Assessment Form	X				X	X	X	X	X	X	X	X	X

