Weight, Height (Screening only), BMI, Waist and Hip Circumference Form	X		X		X	X	X	X	X	X	X	X	X
Vital Signs Form	X		X		X	X	X	X	X	X	X	X	X
Adverse Events Form			X	X	X	X	X	X	X	X	X	X	X
Medication Form	X		X	X	X	X	X	X	X	X	X	X	X
Randomization (ESG vs Hybrid ESG/APC) †		X											
EGD			X							X			
MRI	X										X		
Gastric emptying scintigraphy***	X										X		
Post-enrollment Nutrition/Exertion/Satiety counseling and assessment † †		X			X	X	X	X	X	X	X	X	
Subject Satisfaction Questionnaire													X
Inter-observation of EGD										X			

* Performed by Investigator or delegated medically qualified team member

** Females of childbearing potential only

***POC Urine Pregnancy Test required 48 hours prior to procedure (if not within window from blood test)

+ CBC, electrolytes, BUN, creatinine, HbA1c, fasting blood sugar, fasting insulin, fasting lipids profile (total cholesterol, LDL, HDL, triglycerides), INR, PTT, ALT, AST, ALP, total bilirubin, direct bilirubin, albumin, CRP, B12, ferritin

++Eating and weight patterns questionnaire + hospital anxiety and depression questionnaires (only at baseline), Impact of Weight on Quality of Life-Lite (IWQOL-Lite), Short Form (36) Health Survey (SF36), Patient Health Questionnaire 9 (PHQ9), Pittsburg Sleep Quality Index (PSQI), Three Factor Eating Questionnaire (TFEQ)

† To occur after all screening assessments are complete; within 45 days of screening evaluations

† † To discuss upcoming post-op diet and exertion

◊ If the procedure is unable to be performed within the 105 day in-window range due to factors outside the control of the study team (patient testing positive for COVID-19, delays associated with H. pylori eradication testing, or limitations of the procedural schedule), the PI will assess if any baseline laboratory tests must be repeated prior to the procedure for subject safety.

Participant Retention

All patients will be encouraged to complete study follow-up, and all reasonable efforts will be made to ensure completeness of follow-up.

It is understood that study participants may withdraw consent for study participation at any time irrespective of their reasons. The investigators may also withdraw a participant from the study in order to protect their safety, and/or if they are unwilling or unable to comply with the required study procedures.

In the event of a patient withdrawing from the trial, the reason for withdrawal must be documented on the CRF.

Replacement of withdrawn subjects

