Randomization

After randomization, patients will have a brief post-enrollment nutrition/exertion/satiety counseling and assessment.

Procedure

This includes a patient visit for procedure which may or may not include an admission for a 23-hour observation for symptom management, further elaborated in section 5.5.

Anthropomorphic and vital signs data will also be collected on procedure day.

Post-Op Call

This is a telephone visit which will include review of adverse events and medications.

Week 1

This will include:

- Focused physical examination
- Anthropomorphic and vital signs data
- Review of adverse events and medications
- Nutritional counseling and assessment.

Week 4(Month 1)

This will include:

- Anthropomorphic and vital signs data
- Review of adverse events and medications
- Nutritional counseling and assessment.

Week 8(Month 2)

This will include:

- Anthropomorphic and vital signs data
- Review of adverse events and medications
- Nutritional counseling and assessment.

Week 12 (Month 3)

This will include:

-
- Questionnaires
- Anthropomorphic and vital signs data
- Review of adverse events and medications
- Nutritional counseling and assessment.

Weeks 16, 20

These will include:

- Anthropomorphic and vital signs data
- Review of adverse events and medications
- Nutritional counseling and assessment.

Week 26 (Month 6)

This will be a comprehensive visit, including:

- Complete physical examination
- Anthropomorphic and vital signs data
- Review of adverse events and medications
- Laboratory testing
- Questionnaires
- EGD, to be performed clinically
- MRI
- Gastric emptying scintigraphy
- Nutritional counseling and assessment.
- Inter-observation of deidentified EGD video by qualified endoscopist

Weeks 30, 36, 42, 48

These will include:

- Anthropomorphic and vital signs data
- Review of adverse events and medications
- Nutritional counseling and assessment.

Week 52 (Year 1)

This will include:

- Complete physical examination
- Anthropomorphic and vital signs data
- Review of adverse events and medications
- Laboratory testing
- Questionnaires
- Nutritional counseling and assessment.

Unscheduled Visit

Any unscheduled visits will include a complete physical examination collection of anthropomorphic and vital signs data and review of adverse events and medications.

DATA MONITORING AND SAFETY REPORTING

Data and Safety Monitoring

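### The plan does not say which reading of the week-26 endoscopy is the primary endpoint, and the one reading it describes as blinded has no role in the analysis

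*Combined protocol and SAP*

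**What the plan says.** - **Endpoint.** General Description states: "All participants will undergo a repeat upper endoscopy at 26 weeks (6 months) +/- 2 weeks to evaluate the durability of the endoscopic sutures". The Endpoints list, Power and Sample Size, and section 8.2.1 (Primary Aim) all take the primary outcome from that endoscopy. None names a reader. Section 8.2.1 is a single sentence and also gives no scale or test.
- **External reading.** Trial Intervention says that each subject's 6-month video is "shared with an external center for an additional blinded assessment of the primary endpoint (suture durability) by a qualified endoscopist". The only grading scale in the plan (three levels: intact, partially intact, open) is attached to these videos.
- **Other mentions of that reading.** The Schedule of Events lists it as "Inter-observation of EGD". The Week 26 visit lists "Inter-observation of deidentified EGD video by qualified endoscopist".
- **Site endoscopy.** The Week 26 visit lists "EGD, to be performed clinically" and says nothing about who reads it or whether that person is masked.
- **Blinding.** General Description: "This is a single-center, randomized, single-blinded clinical trial evaluating the efficacy and safety of combined HAPC and ESG". The Randomization section makes participants the blinded party and adds: "Research teams will not be blinded to the randomization results". The assignment "will not be recorded within the EMR to reduce clinical team exposure to their randomized status for follow-up care". The same section has a general sentence about using masking procedures to limit bias, which names no assessor.
- **Analysis.** Power and Sample Size, sections 8.2.1 to 8.2.3 and Missing Data do not mention the external reading, agreement between readers, or a rule for disagreement.

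**The concern.** Deciding whether a suture line is intact, partly intact or open is a subjective judgement, so knowledge of the arm can influence it. The plan allows for two readings of the same endoscopy: one at the site, with no masking requirement, and one external and blinded. It does not say which enters the primary comparison.

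Two risks follow. If the site reading is used, the main result may rest on the judgement of someone who knows which patients had the modified procedure. If the choice is left open, it can be made after both sets of results have been seen. The plan already collects a reading that limits both risks but does not commit to using it for the primary answer.

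**Working it through.** **Step 1. The passages compared.** The plan gives no alpha, primary test, expected rating distribution or effect size for this endpoint, so it has no figure to reproduce. The finding rests on the text.

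| Question | Site reading | External reading |
|---|---|---|
| Named as the primary value? | No | No; called an extra assessment of the primary endpoint |
| Masking required? | No; allocation is kept out of the EMR to reduce exposure | Yes; blinded, de-identified video |
| Grading scale stated? | No | Yes; three levels |
| Role in the statistical section? | Not distinguished; the outcome comes from the repeat endoscopy | None |
| Rule if the two disagree? | None | None |

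**Step 2. Weight of a single reading.** With 12 per arm (Power and Sample Size), one patient is 1/12 = 8.3 percentage points. Start from an assumed 8/12 v 8/12 intact:

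- Two patients reclassified per arm: 10/12 v 6/12, a difference of 4/12 = 33 points, Fisher two-sided p = 0.19.
- Three patients reclassified per arm: 11/12 v 5/12, a difference of 6/12 = 50 points, Fisher p = 0.027. This needs six of 24 readings to move, all in the favourable direction.

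**Step 3. Reader shift, three-level rating (simulation).** Assumptions: identical true ratings in both arms (50% intact, 30% partial, 20% open); tie-corrected rank test, with a result counted when z > 1.96 favouring HAPC; a stated share of ratings moved one level, with no movement beyond the ends of the scale; 200,000 simulated trials per scenario. With no shift the rate is 2.4%.

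| Share shifted | HAPC upgraded only | ESG downgraded only | Both |
|---|---|---|---|
| 10% | 3.4% | 4.2% | 5.8% |
| 20% | 4.7% | 6.9% | 12.1% |
| 30% | 6.5% | 10.8% | 22.6% |

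At a 20% shift under three other true distributions (70/20/10, equal thirds, 30/40/30), the three columns range over 3.6–6.2%, 5.6–9.4% and 11.7–13.5%.

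**Step 4. A second model (exact enumeration).** The rating is reduced to intact v not intact, with a true intact rate p = 50% in both arms. A share b of not-intact HAPC cases is upgraded, so the observed HAPC rate is p + (1 − p)b. For b = 30% this is 0.5 + 0.5 × 0.3 = 0.65. Two-sided rejection at an assumed 5% level rises from 6.4% to 13.4% (Pearson) and from 2.3% to 6.1% (Fisher). Over true rates of 40–70%, b = 30% gives 7.1–16.9% (Pearson) and 2.8–8.1% (Fisher).

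**Step 5. Choosing between two unbiased readings.** Assumptions: the 50/30/20 distribution, and two readers with independent one-level errors in 10%, 20%, 30% or 40% of ratings, truncated at the ends of the scale. The linear-weighted kappa between them is then 0.85, 0.72, 0.60 or 0.50. Taking whichever result favours HAPC more raises the rate from 2.4% for one pre-named reader to 3.4%, 3.8%, 4.1% or 4.3%.

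**The case against.** The strongest reply is that the plan has a recognisable default. Calling the external reading *additional* and an inter-observation suggests that the site endoscopy is the endpoint and the external reading is an inter-observer check. The site endoscopist may also be unaware of the arm, because the endoscopy is performed clinically and the allocation is kept out of the EMR. The Randomization section promises masking measures in general terms. One could even parse the external reading as a further blinded assessment, implying that the first is blinded too. The trial is a small pilot with no power calculation, and MRI gives separate evidence on durability.

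Some of this stands. An unmasked primary reading is possible but not established. The numbers depend on assumed shifts, an assumed rating distribution and a test the plan does not name. The largest rate, 22.6%, needs a 30% shift in opposite directions in both arms at once. The effect of picking between two unbiased readings is small.

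The reply does not remove the point. If the site reading is the default, the primary value is the one with no masking requirement. Keeping the allocation out of the EMR is said only to reduce exposure, and the general masking sentence covers no named assessor. The MRI endpoint is secondary, and no masked reader is stated for it either. A pilot that randomises and compares arms on a named primary endpoint still has to say which measurement that endpoint is.

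**Conclusion.** The concern holds. No section names the reading that supplies the primary endpoint, the only reading described as blinded has no analysis role, no section requires the site reader to be masked, and there is no rule for disagreement. This conclusion comes from the text and needs no assumption.

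The consequence cannot be sized from the documents. Under the assumptions above, a one-level shift in 20% of ratings in one arm roughly doubles or triples the rate of false results favouring HAPC (2.4% to 4.7% or 6.9%). A shift in both arms takes it to about 12%. Choosing between two unbiased readings adds at most about two percentage points. This should be fixed before any comparison by arm. Nothing is irrecoverable, because the blinded reading is collected for every subject.

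**What to change.** In Trial Intervention and section 8.2.1:

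1. State that the external blinded classification of the de-identified week-26 video, on its three-level scale, is the primary endpoint value, and delete the word *additional*.
2. Record the site reading on the same scale and report it as supportive only, with the weighted kappa between the two readings and its weighting scheme named in advance.
3. State that the external classification is entered before any comparison by arm.
4. State that an unreadable or missing video counts as missing in the primary analysis, with the site reading substituted in a sensitivity analysis only. The method needs its own sentence: the hierarchical model in Missing Data is not written out for a single ordinal rating at week 26.

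Other choices, such as consensus or adjudication, would also remove the ambiguity if fixed in advance. Naming the site reading would do so as well, but would leave masking unresolved unless it were also required.

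The cost is mainly protocol and SAP wording, plus possibly one field on the site form, since the scale is now attached only to the videos. There is no added visit or test. There are two downsides: the primary value would depend on one external reader, and visible changes from the three ablation zones (HybridAPC Application) may hint at the arm, so masking is improved but not complete.

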1. ABSTRACT

The obesity epidemic continues to grow in the United States with the prevalence of obesity increasing up to nearly 43% in 2019 with current projections estimating one in every two US Adults by 2030.^{1,2} Obesity is associated with type 2 diabetes, coronary artery disease, chronic joint disease, obstructive sleep apnea, nonalcoholic fatty liver disease (NAFLD), and malignancy. Obesity is associated with an increased risk of all-cause and cardiovascular mortality and accounts for about 2.5 million preventable deaths annually.³⁻⁵ Obesity treatment is limited as lifestyle modifications provide only a modest total body weight loss with a high rate of weight recidivism.⁶ Widely available medical therapies are plagued by intolerance, cost, attenuated response, and weight regain after cessation of pharmacotherapy⁷. Newer GLP-1 analogues while providing significant weight loss require further investigation to determine if the weight loss effect is durable long term.⁸⁻¹¹ Bariatric surgical interventions have been associated with significant side effects, micronutrient deficiencies and weight regain, however they have proven to be the most durable and effective¹². Unfortunately, they are usually unavailable to patients with Class 1 to Class 2 obesity (BMI 30-40 kg/m)¹³. This has led to a significant management gap for patients with mild to moderate obesity. Endoscopic sleeve gastroplasty (ESG) is an endoscopic, minimally invasive intervention that has demonstrated clinically significant, sustained, weight loss ranging between 15-19%.¹⁴ However, given lack of approximation of submucosal structures with ESG to enhance wound healing and fibrogen deposits at the gastroplasty construct, durability of the gastroplasty construct is not maximized¹⁵. We have shown enhanced durability of ESG when combining it with endoscopic submucosal resection techniques¹⁶. However, this is technically challenging and only allows treatment in the distal stomach. Argon plasma coagulation is effective in the transoral outlet reduction (TORe) procedure to help reduce the gastric outlet aperture in patients with weight regain after bariatric surgery by creating a focal coagulation injury in a circumferential manner that ablates the mucosal layer and aids in wound healing¹⁷. One case report evaluation using APC at time of ESG which demonstrated enhanced fibrosis at the site of endoscopically placed sutures potentially improving the durability and of the ESG and reducing complications of more invasive mucosal ablation methods such as endoscopic submucosal dissection or endoscopic mucosal resection techniques.¹⁸ Furthermore, APC application is technically easy with scalable skill-set to the average endoscopist¹⁹. Hybrid APC (HAPC) with submucosal lift offers enhanced safety; especially in ablating the mucosa in the proximal stomach, where the gastric wall is thin, to minimize risk of deep gastric wall injury. While this is hybrid approach is promising, controlled proof of concept evidence is required. Therefore, we propose a pilot randomized control trial evaluating the safety, durability of ESG in combination with HAPC and its effect on weight loss compared against traditional ESG alone in patients with obesity and body mass index (BMI) between 30-40 kg/m².

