Argon plasma coagulation (APC) is a method of non-contact thermal hemostasis initially created to assist in inducing hemostasis⁴³. APC utilizes high-frequency current which applied to the target tissue through an argon plasma jet inducing hemostasis and a homogenous surface coagulation with a limited depth of penetration. This technology has also been used in bariatric endoscopy for patients requiring revision after bariatric surgical procedure⁴⁴. Endoscopic transoral outlet reduction (T0Re) is a commonly performed procedure to help manage weight regain after bariatric surgical intervention⁴⁵. The two most commonly performed techniques for T0Re are full-thickness suturing with plus argon plasma mucosal coagulation (ft-T0Re) and argon plasma mucosal coagulation alone (APMC-T0Re). Both of these techniques utilize APC creates a focal coagulation injury in a circumferential manner causing edema, ulceration and fibrosis reducing the aperture of the gastrojejunal anastomosis.^{46, 47} This causes a physical reduction in the size of the stoma as well as a delay in gastric emptying⁴⁸. One study showed a reduction in the diameter of the gastrojejunal anastomosis of 67% with approximately 15kg weight loss with APC in patients with weight regain after RGYB.⁴⁹ While APC is a useful tool in patients with weight regain following bariatric surgical procedure, it can be combined with ESG to provide enhanced fibrosis along the gastric plications.¹⁸

Clinical Data to Date

ESG was proven to be feasible in human subjects in 2013 and since then it has become the most commonly performed endoscopic bariatric procedure.³⁸ Multiple studies have demonstrated significant and sustained weight loss. However, the durability of the plication construct could be enhanced with addition of HAPC. One case report combined the use of ESG and APC and found to have enhanced fibrosis along the site of endoscopic plications potentially providing an avenue for longer and more durable ESG while minimizing these associated complications. Furthermore, with enhanced fibrosis this could decrease the incidence of weight regain in patients undergoing ESG and capitalize on the metabolic benefits of gastric mucosal revitalization reported with APC alone. However, to date no prospective controlled studies have been done comparing traditional ESG to a hybrid ESG and APC procedure.

Rationale

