Patients withdrawn prior to undergoing combined HAPC and ESG or ESG alone will count towards the target accrual. Screen failed patients will not count towards target accrual. New patients will be randomized to target accrual of 24 total patients receiving combined HAPC and ESG or ESG alone. The power and sample size calculation includes sufficient patients to yield power assuming some post-intervention dropout.

Source Documentation

Study source worksheets and/or electronic documentation in the medical record will be used as source documentation for the trial for all participant follow-up visits. Source documentation from the electronic medical record will be required for the procedure(s), medications, and any serious adverse medical events. REDCap will be used for collection of electronic sources and verified by PI attestation as the eCRF. If unavailable to conduct electronic source, physical CRF source worksheets will be available and can be added to the eCRF for investigator attestation.

PROTOCOLS FOR PROCEDURE AND IMAGING

HybridAPC (HAPC) Application

HAPC will be performed in conjunction with ESG in patients in the treatment group. The location is from the level of the incisura all the way to the fundus. The pattern includes 3 rectangular APC ablation zones created on the anterior, greater curvature and posterior surface of the stomach. The HAPC is composed of a submucosal lift followed by ablation. The default setting of the APC is 50 Watts, 1 L/min flow, but it may be adjusted within normal clinical limits dependent on participant anatomy and tissue response. After ablation, ESG will be performed in standard fashion.

Measurement of Gastric Accommodation by Dynamic MRI

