8.2.1 Primary Aim

The primary outcomes are durability of plications and endoscopic sutures on repeat endoscopy at 6 months, in the two randomized arms.

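### The blinded week-26 video grade draws on gastric tissue appearance as well as sutures, with no rule for combining them, and HAPC is meant to change that tissue in one arm only

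*Combined protocol and SAP*

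**What the plan says.** The Trial Intervention section has each subject's de-identified 6-month EGD video shared with an external centre for an "additional blinded assessment of the primary endpoint (suture durability) by a qualified endoscopist". The grading rule follows: "Each video will be classified objectively according to the aspect of the gastric tissue and the sutures (intact, partially intact, or open". No definition of the three levels is given.

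Section 8.2.1 words the endpoint more widely: "The primary outcomes are durability of plications and endoscopic sutures on repeat endoscopy at 6 months, in the two randomized arms". It names no scale and no test. The Missing Data section mentions a hierarchical regression model for the primary analysis, but not how a three-level grade would enter it.

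On the treatment, the General Description gives the aim of HAPC before suturing as "enhanced fibrosis along the site of the plications potentially providing an avenue for longer and more durable ESG". The HybridAPC Application section places the ablation between the incisura and the fundus: "The pattern includes 3 rectangular APC ablation zones created on the anterior, greater curvature and posterior surface of the stomach". Control patients have ESG alone.

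The Randomization section leaves the research teams unblinded. The external video reading is the only assessment of durability that the plan describes as blinded.

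**The concern.** De-identification removes the patient's name from the video but not the treated tissue. If ablation leaves a recognisable mark, the reader may learn the arm from the very feature the rule asks them to look at. The grade could then move for two reasons unrelated to whether the construct held: expectation once the arm is suspected, and direct scoring of the tissue change itself.

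The primary endpoint is a judgement on three undefined levels in 12 versus 12 patients. The local team knows the arm, so if the external reading is unmasked, no masked assessment of the primary endpoint by endoscopy is left. The Abstract presents the trial as controlled proof of concept, so a distorted estimate would carry into whatever follows it.

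**Working it through.** **No figure to reproduce.** The Power and Sample Size section gives 12 + 12 = 24 patients and no power, alpha, effect size or event rate. The check is therefore mainly a comparison of passages.

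**Step 1: is tissue an input to the grade?** Yes. The grading sentence names it beside the sutures, although the sentence before it calls the endpoint suture durability.

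**Step 2: does treatment act on that input in one arm only?** Yes, by intent. Fibrosis along the plications is the stated aim of HAPC (General Description), and only the treatment arm receives it.

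**Step 3: do the documents show the effect is visible at 26 weeks?** No. The Abstract says that one case report of APC with ESG "demonstrated enhanced fibrosis at the site of endoscopically placed sutures", and Clinical Data to Date repeats this. The Background describes APC at the gastric outlet after bypass as "causing edema, ulceration and fibrosis reducing the aperture of the gastrojejunal anastomosis". Neither describes the endoscopic appearance of HAPC plus ESG at 26 weeks.

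**Step 4: does anything separate tissue from suture status, or test the masking?** No. There is no separate suture score, no combination rule and no record of the reader's guess of the arm.

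**Step 5: scale.** One patient in an arm of 12 is 1/12 = 8.3 percentage points.

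To see what misgrading could do, assume:
- the grade is reduced to intact versus not intact;
- the true intact rate p is equal in both arms;
- a fraction u of non-intact HAPC videos is graded intact because of tissue appearance;
- the test is a two-sided Pearson chi-square at 0.05 (borrowed from the binary outcomes in section 8.2.2).

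The recorded HAPC rate is p + u(1 − p), so the false difference is u(1 − p). Exact enumeration of two Binomial(12) arms gives:

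| p | u | False difference (points) | Chance of a significant result favouring HAPC |
|---|---|---|---|
| 0.5 | 0 | 0 | 3.2% |
| 0.5 | 0.1 | 5 | 5.4% |
| 0.5 | 0.3 | 15 | 12.9% |
| 0.5 | 0.5 | 25 | 26.3% |
| 0.3 | 0.5 | 35 | 45.9% |
| 0.7 | 0.5 | 15 | 12.1% |

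All values of p and u are assumed, and u = 0 is as compatible with the documents as any other. The direction is assumed too. If 30% of intact HAPC videos were graded down at p = 0.5, the false difference would be −0.3 × 0.5 = −15 points, with the same 12.9% chance of significance in favour of ESG alone. In a pilot of this size the main harm would be a biased estimate rather than a false significant result.

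**The case against.** The strongest reply is that aspect of the gastric tissue means whether the plication is still closed. The three levels describe closure, not scarring. The endpoint in the General Description and section 8.2.1 covers plications as well as sutures, and plications are folded gastric tissue. On this reading the rule is nearly right already. The sentence may also intend two gradings rather than one combined category. Both readings are possible, but the text does not choose between them.

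Second, fibrosis is the proposed route to durability, so a tissue effect is not pure artefact. This stands in part. A plication held closed by fibrosis is durable and should count. But grading closure captures that benefit, whereas crediting scarring directly assumes the hypothesis under test.

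Third, MRI at baseline and 26 weeks offers a second view of gastroplasty durability that does not rest on mucosal appearance. That helps interpretation, but MRI is a secondary endpoint.

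A reader might go further and infer that the endoscopist will recognise the arm, that the bias must favour HAPC, or that videos are read one at a time without calibration. The documents support none of these. Visibility at 26 weeks is not documented, and ablation precedes suturing, so treated surfaces may lie within the folds. Edema or ulceration, reported for APC elsewhere, could lower a grade. The plan says when videos are shared and is silent on when, or in what order, they are read.

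**Conclusion.** The concern holds as a gap in the outcome definition and its masking. Tissue appearance is a named input to the grade, HAPC is intended to alter that tissue in one arm, and nothing separates the two or checks the masking. The word objectively has no scoring criteria behind it.

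The size and direction of any bias are unknown. The one firm figure is 8.3 points per reclassified patient. A statement such as two or three patients upgraded, giving 2/12 = 17 to 3/12 = 25 points, only restates an assumption and should not be read as an estimate.

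A related gap affects the remedy. The external reading is called additional, and the Schedule of Events lists it as an inter-observation. No rule says whether it or the unblinded local reading is the primary result. Improving the external form achieves little unless that is settled.

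**What to change.** On the external reading form:

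1. Grade suture and plication integrity first (intact, partially intact, open), with each level defined and an instruction to disregard scarring and mucosal appearance. Lock this item before going on.
2. Record tissue or fibrosis appearance afterwards, as a descriptive item only.

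In section 8.2.1, state that the locked external blinded item is the primary durability outcome. Show the MRI gastroplasty measure alongside it.

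Optionally, read all videos in one random-order batch after the last week-26 EGD, and have the reader record a guess of the arm. Report the guess descriptively. With 24 videos, 17 correct are needed for a one-sided p of 0.032 under pure guessing. By the binomial, a reader who is truly 70% accurate reaches 17 only 56% of the time, and one who is 60% accurate 19% of the time. A guess made after grading also mixes unmasking with belief that HAPC works.

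The cost is a revised form, one sentence in the analysis section and, if batched, later reading. No extra reader or procedure is needed. The form fits either meaning of tissue aspect. Residual unmasking may remain, and the guess would only partly reveal it.
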